**Outcomes Assessment.** Follow-up assessments for 512 participants will be conducted by interviewers blinded to the treatment allocation at 3, 6, 9, and 12 months. Outcome measures will be assessed by telephone interview, and EHR data will be reviewed for all patients with asthma in both study arms. Given the minimal risk of survey questions and the importance of having full datasets for study analyses, in the case that study personnel are unable to reach the caregiver who signed consent at enrollment (after multiple phone attempts, letters, home visits, and scheduled appointment outreach), we will proceed to obtain verbal consent and survey data from another caregiver who is aware of the enrolled child's history with asthma. These caregivers include the other parent, guardian, grandparent, aunt, or uncle. Name and contact information of the alternate caregiver will have been provided at enrollment by the caregiver who initially signed consent.

**Measures:** The following measures are organized by clinic-, provider- and patient-level variables.

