## B. Subjects and Setting

Outpatient practices (n=22) that are part of Montefiore Health System will participate in the study (see Letter of Support). These 22 practices are located throughout the Bronx, NY, represent different practice types, and have participated in several of our prior studies (Table 3). Though there were initially 22 proposed outpatient practices, two practices were closed, two practices (FCC-B and FCC-C) were combined as a single site given that they serve patients in the same facility, and one practice was excluded given no pairing available, resulting in a total n=18 participating outpatient practices. The number of children with asthma across practices (N=10,109) of whom we estimate ~ 50% (N=5,000) to have persistent or uncontrolled asthma is sufficient to meet our sample size needs. A subset of 512 children will be recruited over 4 years (~128 participants each year) to obtain clinical outcomes data that are not in the EHR.

Table 1. Primary Care Practices*					
Site	Practice Type	Provider Type	# 2-12yr olds in practice	# 2-12yr olds with asthma	# visits for 2-12yr olds with asthma
Astor Avenue	NHC	Pediatrics	3,075	576	1,012
Bronx East	NHC	Pediatrics	4,775	884	1,516
Burke Avenue	NHC	Pediatrics/Family MD	1,102	117	196
Castle Hill	FQHC	Family MD	814	97	135
CFCC	FQHC	Pediatrics	5,791	1,144	1,824
CHCC	FQHC	Pediatrics	4,658	1,332	2,488
Co-op Bartow Ave	NHC	Pediatrics	2,485	634	1,059
Eastchester	NHC	Pediatrics	1,350	325	703
FCC - B	Hospital Clinic	Pediatrics	3,671	684	1,028
FCC - C	Hospital Clinic	Pediatrics	3,470	805	1,300
FHC	FQHC	Family MD	1,739	339	606
Grand Concourse	NHC	Pediatrics/Family MD	3,133	540	868
Grand UCC	NHC	Pediatrics/Family MD	2,950	235	262
HIP Cross County	NHC	Pediatrics/Family MD	3,058	272	385
MAP-8	Hospital Clinic	Pediatrics	2,935	631	1,551
Marble Hill	NHC	Pediatrics/Family MD	1,143	186	294
University Avenue	FQHC	Pediatrics/Family MD	1,697	344	645
Verde Clinic	NHC	Family MD	359	78	146
Wakefield	NHC	Pediatrics	354	309	600
West Farms	FQHC	Family MD	954	215	368
White Plains Road	NHC	Pediatrics/Family MD	1,204	174	273
Williamsbridge	FQHC	Family MD	1,059	188	308
TOTAL	-	-	51,776	10,109	17,567

FQHC=Federally Qualified Health Center; NHC=Neighborhood Health Center. \*Number of patients seen between 1/1/14-12/31/14

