Enrollment goals for each practice will be based on the number of children with asthma seen at the practice. Since enrollment will occur over an extended time period, we will block enrollment by site pair to assure an equal balance of children in each group for each seasonal time period. Research staff will be present in each clinic 2-3 days/week for recruitment, until monthly enrollment goals are met for that practice. We will review the practice's schedule the day before to determine if potentially eligible participants are scheduled for a visit. Research staff will call patients with asthma ages 2-12 years and ask families to come to their appointment with physician 30-60 minutes earlier to be screened by the nursing staff for asthma severity. If eligible, the caregiver/child will be informed about the study, undergo the informed consent process and complete baseline survey prior to seeing the physician. Recruitment goals will be reviewed weekly for each practice and adjustments of staffing made as needed. Days for recruitment will vary to ensure that patients of providers who are in clinic on certain days of the week are not over- or under-sampled (see Recruitment Protocol, Appendix A). Following informed consent/assent, research staff will conduct a 10-minute survey with the primary caregiver in the waiting room to obtain *baseline measures* of enrolled participants. All survey instruments will be available in English/Spanish and questions will be read aloud. Caregivers will be offered a private location within the waiting room to complete the survey. The baseline measures include standard demographic and health history variables, healthcare utilization, quality of life, beliefs about medication and adherence (Appendix A).

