### **Summary of Analytic Plan:**

We will use graphical and numerical summaries to describe the outcomes at each assessment point. If distributional assumptions for particular statistical procedures are violated, appropriate transformations will be made or non-parametric tests will be used. All primary and secondary analyses will follow the intent-to-treat principle; all participants will be analyzed in the group to which their clinic was assigned irrespective of their post-randomization behavior, and all participants will be analyzed using multiple imputation techniques. Hypothesis-driven comparisons will be made with control of the type I error rate at 0.05 (two-sided).

**Preliminary Analysis.** We will examine data for out of range values. Descriptive statistics will be generated regarding practice characteristics such as size (small, medium, large), practice type (hospital-based practice, Federally Qualified Health Center, neighborhood health center), and patient mix (pediatrics, adult/pediatrics) to help to understand the sample as well as the generalizability of study findings. We will determine whether there are differences at baseline between the eMPI and eUC providers and patients in demographics and background characteristics. This will include analogs of t-tests (or Wilcoxon rank sum tests) for continuous variables and chi-square (or Fisher's Exact) tests for categorical variables adjusted by generalized estimating equation (GEE) methods for the clustering induced by providers within clinics.

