Missing data: Every effort to retain participants in the study will be exerted in order to avoid bias due to attrition. For those individuals who refuse continued participation, we will document reasons for study discontinuation and Rubin's multiple imputation method with 5 repeated imputations will be employed to impute the missing endpoint for conducting the intent-to-treat analysis.

**Power Analysis.** With a recruitment of 512 participants at baseline, we anticipate a final sample of 460 participants with complete data for the primary analysis assuming no more than 10% attrition at 12 month evaluation. This estimate of attrition rate is conservative based on our prior experience. To account for the intra-cluster correlation due to cluster sampling, we estimate that an intra-provider correlation coefficient is no greater than 0.03 from our prior studies. Although the intra-practice correlation coefficient should be smaller than intra-provider correlation coefficient, we conservatively used the same value (i.e., 0.03). Under the above assumption, with 230 participants per group, we will be able to provide 80% power to detect a standardized effect size of  $\geq 0.29$  in change of number of SFDs. Even if actual attrition is greater than we expect (e.g., 15%), the detectable standardized effect size will only increase slightly to 0.30. Further, as we will impute missing data using informative covariates for the primary analyses, the power to detect such effects will be  $>80\%$ .

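### Aim 2 power for symptom-free days: the stated inputs give about 66-69% at 0.29, not 80%, even with equal clusters, and size-based enrolment goals lower it further

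*Combined protocol and SAP*

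**What the plan says.** Under Aim 2, Power Analysis, the plan recruits 512 children and says "we anticipate a final sample of 460 participants with complete data", "assuming no more than 10% attrition at 12 month evaluation". It takes the provider ICC from prior studies as at most 0.03, and adds: "Although the intra-practice correlation coefficient should be smaller than intra-provider correlation coefficient, we conservatively used the same value (i.e., 0.03"). It concludes that "with 230 participants per group, we will be able to provide 80% power to detect a standardized effect size of" 0.29 or more, rising to 0.30 at 15% attrition. A last sentence begins "Further, as we will impute missing data using informative covariates for the primary analyses" and ends by claiming power above 80%. The section gives no number of clusters, cluster size, design effect or measure of variation in cluster size.

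The number of children per practice is set elsewhere. Section B, in the enrolment procedures for the subset of 512, says: "Enrollment goals for each practice will be based on the number of children with asthma seen at the practice". Table 1 lists those counts for 22 sites. The same section then reduces the trial to 18 practices: two closed, one had no pair, and "two practices (FCC-B and FCC-C) were combined as a single site given that they serve patients in the same facility". The Aim 2 analysis is a GEE meant to account for correlation within provider and within practice; no working correlation is named.

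**The concern.** Two things look wrong. The first is that 0.29 seems too small for an ICC of 0.03 acting on practices of 20 or more children. The second is that goals tied to practice size make the clusters very unequal. Large clusters add little information when outcomes are correlated within practice, so a calculation that ignores the inequality overstates power.

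SFD change is the main clinical outcome, although it is a secondary hypothesis. If the planning power is overstated, a null SFD result may be taken as stronger evidence of no benefit than the design can supply. The imputation sentence adds to this, because the limit comes mainly from how the children are spread over practices and not from missing endpoints.

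**Working it through.** **Inputs.** Two-sided alpha 0.05 (Summary of Analytic Plan: "Hypothesis-driven comparisons will be made with control of the type I error rate at 0.05 (two-sided")); 460 analysed, 230 per arm; practice ICC 0.03 (Aim 2, Power Analysis); 22 practices planned, 18 taking part, and the asthma counts of Table 1 (Section B); about 200 providers (Background). Standardized scale, so SD = 1. Normal approximation, which favours the plan: a t reference with 16 df takes the 18-equal-practice power below from 66% to 60%.

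**Formulas.** DE is the design effect, m the mean cluster size, m_k the size of cluster k, N the total analysed.
- Detectable effect at 80% power = 2.80 x sqrt(2 x DE / 230)
- Power at 0.29 = Phi(0.29 x sqrt(230 / (2 x DE)) - 1.96)
- Equal clusters: DE = 1 + (m - 1) x ICC
- Unequal, independence: DE = 1 + [(1 + CV^2) x m - 1] x ICC
- Unequal, efficient exchangeable weighting: DE = N / sum[m_k / (1 + (m_k - 1) x ICC)]

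**Step 1: the plan's own figure.** With no clustering the detectable effect is 2.80 x sqrt(2/230) = 0.261. The stated 0.29 therefore implies DE = (0.29/0.261)^2 = about 1.23, and at ICC 0.03 that means m = 1 + 0.23/0.03 = about 8.7 children per cluster. This matches neither provider clusters (460/200 = 2.3, DE 1.04, detectable effect 0.27) nor practice clusters (460/22 = 20.9). The figure could not be reproduced from the stated inputs.

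**Step 2: equal practices, ICC 0.03.**
- 22 practices: DE = 1 + 19.9 x 0.03 = 1.60; detectable effect 0.330; power at 0.29 = Phi(2.46 - 1.96) = 69%.
- 18 practices: m = 460/18 = 25.6; DE = 1 + 24.6 x 0.03 = 1.74; detectable effect 0.344; power = Phi(2.36 - 1.96) = 66%.

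**Step 3: goals proportional to Table 1 (an assumption).** The 22 counts sum to 10,109, run from 78 to 1,332, and have CV 0.73. For 18 practices, FCC-B and FCC-C are merged (684 + 805 = 1,489). The three other departures are not named, so all 1,140 ways of removing 3 of the remaining 20 sites were run. CV is then 0.73 to 0.94, and the largest practice supplies about 70 to 101 of the 460 children. At the lower end, independence gives DE = 1 + [(1 + 0.73^2) x 25.6 - 1] x 0.03 = about 2.15.

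| ICC 0.03, 460 analysed | DE | Detectable effect | Power at 0.29 |
|---|---|---|---|
| 22 equal | 1.60 | 0.330 | 69% |
| 22 proportional, exchangeable | 1.80 | 0.351 | 64% |
| 22 proportional, independence | 1.94 | 0.363 | 61% |
| 18 equal | 1.74 | 0.344 | 66% |
| 18 proportional, exchangeable | 1.95-2.08 | 0.365-0.377 | 58-60% |
| 18 proportional, independence | 2.15-2.42 | 0.383-0.407 | 52-56% |

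**Step 4: the share due to unequal size.** With 18 practices, the fall from 66% is about 5-8 points under exchangeable weighting and about 9-14 under independence. Now set the ICC to 0.0117, so that 0.29 is exact for 22 equal practices. Unequal size alone then takes 80% to 76-77% with 22 practices, a loss of 3-4 points. With 18 practices the figures are 78% equal and 70-75% proportional.

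**Step 5: imputation.** Suppose imputation recovered the full information of all 512 children, its best case. With 18 proportional practices at ICC 0.03, power at 0.29 would still be only 53-63%.

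**Step 6: dependence on the ICC.**

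| Practice ICC | 18 equal, power at 0.29 | 18 proportional, both weightings |
|---|---|---|
| 0.005 | 84% | 80-82% |
| 0.01 | 80% | 73-76% |
| 0.03 | 66% | 52-60% |

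**The case against.** A reader might infer that unequal cluster size is why the 80% fails. The documents do not support that. At the plan's own ICC, power is already 69% or 66% with equal clusters, so most of the shortfall with 22 practices comes from a detectable effect that does not match its inputs. The top of the 5-14 point range also needs an independence working correlation, and the plan names none.

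Strict proportionality is likewise a reading of the rule. Goals are only said to be based on the counts, with no formula, floor or cap. The plan also recruits about 128 children a year and brings in 4-6 practices a year, which could even out the clusters. A simulation of size-matched pairs assigned at random to four waves of 128, proportional within wave (again an assumption), gave a median CV of 0.56 and median power of 60-62%. That narrows the loss from unequal size to about 4-6 points but does not restore 80%.

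A reader might also infer that the trial is underpowered whatever the ICC. That does not follow. The plan gives 0.03 as a ceiling for providers and expects the practice value to be smaller; at 0.005 the claim about holds. If only provider clustering mattered, power would be 84-86%. But the plan says it used 0.03 for practices, practices are the randomized unit, and the analysis includes practice-level correlation. Matching may recover some precision; the documents give no figure for it.

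Finally, SFD is a secondary outcome, no test changes, and the confidence interval will reflect the actual clusters provided the GEE accounts for practice. This limits the consequence, but the power statement is still wrong as written.

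**Conclusion.** The concern holds in this form: 80% power at 0.29 does not follow from 230 per arm and a practice ICC of 0.03, and the size-based enrolment rule, for which no allowance is made, makes the shortfall larger. For the 18 participating practices, the detectable effect at ICC 0.03 is about 0.34 with equal clusters and about 0.37-0.41 with proportional goals. Unequal size is a contributing cause, not the main one. The claim that imputation lifts power above 80% fails at the same ICC.

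These figures rest on ICC 0.03 for SFD change, goals proportional to Table 1, children split evenly between arms, no gain from pairing, and a normal approximation. The conclusion is sensitive chiefly to the ICC. The correction is worth making because SFD is the main clinical outcome.

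**What to change.** In Aim 2, Power Analysis:
- State the number of practices (18), the mean cluster size, the practice ICC, and the CV of the enrolment goals actually set.
- Recompute with an unequal-cluster design effect, either of the two forms given above, matched to the working correlation chosen for the GEE.
- Replace 0.29 and 0.30 with the result, shown over a range of ICC. At 0.03 this is about 0.34 if goals are equal and about 0.37-0.41 if proportional.
- Delete the sentence saying that imputation takes power above 80%.

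The cost is a few lines of text and a less favourable stated detectable effect. No extra children are needed and the analysis is unchanged.

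Flatter goals for practices still to enrol are optional and not needed for the correction. Goals proportional to the square root of size would bring the CV to about 0.42 and the design effect to about 1.8-1.9, at the price of slower accrual in small practices.
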